## 5.2 Hypothesis

**H1:** Average patient weight is at least 2.5 kg lower in the partner-assisted arm than the patient-only arm at 24 months.

**H2:** Average daily caloric intake are significantly lower, and frequency of moderate intensity physical activity is significantly greater, in the partner-assisted arm than the patient-only arm at 24 months.

**H3:** Interdependence constructs (transformation of motivation, couple efficacy, outcome efficacy, use of communal coping) mediate the effect of the partner-assisted weight management intervention on weight loss.

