## 7. Study Design and Endpoints

### 7.1 General Design

In this two-arm RCT, 230 couples (460 total) will be randomized to patient-only or partner-assisted intervention. In both arms, intervention will be delivered for 18 months followed by 6 months of no intervention contact in order to evaluate sustainability of effects. The primary endpoint is weight measured at 24 months (Figure 2).

Figure 2. Study Flow

This design addresses long-term weight loss, which results from both initial weight loss and weight loss maintenance. Because social support is important for initiation and maintenance, incorporating partners in both phases is likely to have greater impact on long-term weight loss than incorporating partners in either phase alone. The patient intervention is identical between arms. The partner-assisted arm involves additional content, which increases the amount of each intervention contact. This is by design, as the partner-assisted intervention involves teaching couples to communicate about health and engage in cooperative action. Equalizing dose in both arms would require removing portions of the efficacious patient intervention in the partner-assisted arm or adding unrelated content to the patient-only arm, neither of which would provide a stringent test of the partner intervention.

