#### 7.1.1 Primary Study Endpoints

The primary outcome is long-term weight loss, defined as patient weight at 24 months.

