### 10. Study Analysis

#### 10.1 Sample Size Determination

The sample size estimate is based on the primary hypothesis that estimated patient weight will be at least 2.5 kg lower at 24 months in the partner-assisted than patient-only arm. This effect size was chosen because smaller differences are unlikely to be considered meaningful to researchers, providers, or patients.(78) The sample size was determined by multiplying the number of participants required for a t-test of post scores by 2(1-p) and adding one extra participant per arm.(79) Based on MAINTAIN, we anticipate a common standard deviation of 19.9 kg and a correlation (p) between the *month0* and *month24* time points of 0.96. Thus, we need 160 participants total (80 in each arm) to detect a 2.5 kg difference with 80% power and a type-I error rate of 5%. We further inflate the sample size to 1) incorporate the intra-class correlation (ICC) of small group members into consideration and 2) compensate for attrition using procedures for group-randomized designs.(66) Let  $m=15$  (conservative upper limit) be the number of patients in each of the small groups, and let  $ICC=0.01$  represent the intra-class correlation between patients in the same group. The updated sample size is  $n = 160 * [1 + (m-1)ICC]$ , or 180. We then conservatively inflate the sample size for an attrition rate of 20% through month24. Therefore, we will enroll  $n=230$  patients (115 per arm), randomized to receive the partner-assisted or patient-only intervention, to detect a 2.5 kg difference in mean 24-month net weight loss between arms.

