**Aim 1: Test the hypothesis that average patient weight is at least 2.5 kg lower in the partner-assisted arm than the patient-only arm at 24 months.** The unit of time will be months relative to randomization. The outcome is weight measured at each in-person study visit. Therefore, *month0* represents the weight at the point of randomization (i.e., the first group visit), and *month24* represents the primary study endpoint. The between-arm comparison in net weight loss from *month0* to *month24* will be examined with a multilevel longitudinal model(80) of the general form:  $Y_{ijt} = X_{ijt}\beta + c_j + Z_{ijt}b_{ij} + \varepsilon_{ijt}$ , where  $Y_{ijt}$  is weight in kg for patient  $i$  in small group  $j$  at  $t=month0, 6, 12, 18, 24$ . The predictors in the model will ( $X_{ijt}$ ) include a time main effect, the intervention main effect, and the intervention arm by time interaction, and  $Z_{ijt}$  will include an intercept and a time effect. We will use a flexible polynomial model for the main effect of time and keep the treatment by time interaction linear in time. We will first explore cubic time effects. If it is inadequate for the complexity in the temporal trend, higher order polynomials will be explored. We will formally check for the adequacy of a particular form for time effects using Wald or likelihood ratio tests for higher-order terms. The effect  $c_j$  is an additional random intercept for small group  $j$ , capturing common effects at the small group level. The predictor vector  $X_{ijt}$  will also include indicator variables for each of the eight strata defined by the cross-classification of the stratification variables of patient sex, patient BMI, and partner BMI. As a first step, the correlation of patients' repeated measures over time will be modeled and accounted for via the patient-level random intercept and time slope,  $b_{ij}$ . However, as is advised by good modeling practice,(80) various covariance structures for time will be explored, including unstructured and differential correlation structures by arm, via graphics such as the variogram and estimation with ReML,(81) all while being blinded to treatment effects. The AIC and BIC fit indices will be used to choose the best correlation structure. We will estimate the parameters in the model using the SAS procedure MIXED (Cary, NC). To test the null hypothesis that the average weight is equal in the two intervention arms, we will test if the coefficient for the time by treatment interaction is zero. Specifically, if  $X_{ijt}\beta$  takes the following form  $\beta_0 + \beta_1 trt + \beta_2 time + \beta_3 trt * t + \beta_4 covariates$ ,

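### The primary test is a treatment-by-linear-time slope, which is guaranteed to match the month-24 difference the trial defines and powers only if the arms diverge in a straight line

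*Combined protocol and SAP*

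**What the plan says.** The target is stated consistently. Section 7.1.1: "The primary outcome is long-term weight loss, defined as patient weight at 24 months". Section 5.2, H1: "Average patient weight is at least 2.5 kg lower in the partner-assisted arm than the patient-only arm at 24 months". The calculation in section 10.1 uses only months 0 and 24 and their correlation, and sets the trial's size "to detect a 2.5 kg difference in mean 24-month net weight loss between arms". The Aim 1 text in section 10.2 also describes the comparison as net weight loss between months 0 and 24.

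The model in section 10.2 lets the common time trend be cubic or of higher order, but it will "keep the treatment by time interaction linear in time". The test is then: "we will test if the coefficient for the time by treatment interaction is zero". The null hypothesis is written as beta3 = 0 on treatment multiplied by linear time.

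Two other provisions bear on this. The plan says "We will formally check for the adequacy of a particular form for time effects using Wald or likelihood ratio tests for higher-order terms", but this follows the sentence that makes the interaction linear, so as written it does not relax it. The covariance starts as a random intercept and slope, alternatives are explored blind to treatment effects, and "The AIC and BIC fit indices will be used to choose the best correlation structure". The sensitivity analyses in section 11.2.2.1 concern missing data, and one of them refits the same model. Aim 2 uses the Aim 1 methods.

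**The concern.** A slope coefficient summarises the arm difference over all five visits. Multiplied by 24, it is sure to equal the difference in month 0-24 change only when the true difference grows in proportion to time. No document gives the expected shape of the arm difference, and linear growth cannot be taken for granted. Live partner contact is front-loaded (section 9.2.2): six meetings in months 1-6, three group sessions and three calls by month 9, then calls in months 12 and 18. That is 12 of 14 contacts by month 9 and none in months 19-24.

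So the estimate and p-value reported for H1 may not describe the month-24 difference, and the error can go either way. The same true month-24 difference can also be reported differently depending on a covariance structure chosen later.

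There is a further consequence for the last phase, which section 7.1 describes as "6 months of no intervention contact in order to evaluate sustainability of effects". A linear interaction forces the month-18 difference in change to be 18/24 = 75% of the month-24 one, so it cannot show an effect fading over months 19-24. The only other tool in the supplied text is descriptive trajectory plots.

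**Working it through.** **The plan's own figure.** Inputs from section 10.1: SD 19.9 kg, correlation 0.96, difference 2.5 kg, 80% power, 5% type I error (taken as two-sided), m = 15, ICC 0.01, 20% attrition.

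- t-test of post scores: 2 × (1.960 + 0.842)² × 19.9² / 2.5² ≈ 995 per arm.
- × 2(1 − 0.96) = 79.6, so 80 per arm, 160 in total (162 with the extra participant per arm).
- Design effect 1 + 14 × 0.01 = 1.14; 160 × 1.14 = 182.4 (stated 180).
- 182.4/0.8 = 228, or 180/0.8 = 225 (stated 230).

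The sample size therefore reproduces within 3%, from a comparison of months 0 and 24 only.

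**What the slope test estimates.** Let d be the vector of arm differences at months 0, 6, 12, 18, 24 (positive = partner-assisted arm lighter), S the covariance matrix of their estimates, and Z the matrix with columns 1 and t. With equal arms, generalised least squares gives (Z′S⁻¹Z)⁻¹Z′S⁻¹d. The slope element × 24 is the reported effect, whatever the order of the common trend (checked for orders 1 to 4). The alternative is the contrast d24 − d0 from a model with arm by categorical visit.

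Covariance for the starting model:
- Variance of month 0-24 change = 2 × 19.9² × 0.04 = 31.68 kg².
- Slope variance = (31.68 − 2s²)/576, with equal variances at months 0 and 24.
- The residual SD s is not in the documents; s = 1.5 and 2.5 kg are assumed.
- S is multiplied by 1.14; rejection rates use the normal approximation.

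Main case: 115 per arm, dropout completely at random, 5.75 per arm last seen at each of months 0, 6, 12 and 18, and 92 complete.

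| | s = 1.5 | s = 2.5 |
|---|---|---|
| Weights on d0, d6, d12, d18, d24 | −0.92, −0.31, 0.10, 0.42, 0.72 | −0.87, −0.36, 0.07, 0.42, 0.74 |
| SE of 24 × beta3 | 0.826 | 0.817 |
| SE of month-24 contrast | 0.837 | 0.851 |

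All paths below are assumptions. Ranges cover both values of s.

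| Path of arm difference (months 6, 12, 18, 24), kg | True at month 24 | 24 × beta3 | Rejection, slope | Rejection, contrast |
|---|---|---|---|---|
| 1. 2.5, 2.5, 2.5, 2.5 | 2.5 | 2.2-2.3 | 76-80% | 84-85% |
| 2. 4, 3.5, 3, 2.5 | 2.5 | 1.9-2.1 | 65-74% | 84-85% |
| 3. 1.25, 1.9, 2.3, 2.5 | 2.5 | 2.50-2.55 | 86-87% | 84-85% |
| 4. 1.07, 2.32, 2.5, 2.5 | 2.5 | 2.7 | 91% | 84-85% |
| 5. 0, 0, 2.5, 2.5 | 2.5 | 2.8-2.9 | 93-94% | 84-85% |
| 6. 0.83, 1.67, 2.5, 1.25 | 1.25 | 1.8 | 59-61% | 31-32% |
| 7. 2.5, 2.5, 2.5, 1.25 | 1.25 | 1.25-1.41 | 34-40% | 31-32% |
| 8. 1, 2, 3, 0 | 0 | 1.0-1.1 | 25-28% | 5% |

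Path 4 is proportional to cumulative live partner contacts: 2.5 × (6, 13, 14, 14)/14. In path 6 the fitted gap widens by 1.8 × 6/24 = 0.45 kg over months 18-24 while the true gap narrows by 1.25 kg. Path 8 rejections are not false positives under a null of equal mean weights throughout, because the arms do differ earlier, but they could be read as a month-24 benefit that is absent.

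**Dependence on covariance and dropout.**

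- Complete data, 92 per arm, starting model: weights −0.8, −0.4, 0, 0.4, 0.8. Path 1 gives 2.0 kg and 63-65% (contrast about 80.5%); path 7 gives 1.0 kg.
- AR(1), complete data: weights −1, 0, 0, 0, 1, so no error on any path.
- AR(1), evenly spread dropout: weights −1.08, 0.06, 0.06, 0.06, 0.92. Path 1 becomes 2.7 kg, path 5 becomes 2.43 kg, and path 8 is rejected about 7% of the time.
- Path 1, starting model, with all dropout at one time: after month 0, 2.0 kg and 63-66%; after month 6, 2.3-2.6 kg and 77-86%; after month 12, 2.3-2.4 kg and 81-86%; after month 18, 2.2 kg and 79%.

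**The case against.** The strongest reply is that the plan names the right target and estimates it with a prespecified one-degree-of-freedom slope, a recognised choice. If the arms never differ, type I error is nominal. The harm rests on paths that no document predicts. The one path built from the documents, path 4, gains power and is off by only about 0.2 kg. Section 7.1 argues that involving partners in both initiation and maintenance gives more long-term effect than either alone, and partner text messages continue, tapering, to month 18. Both suggest a gap that keeps growing after month 6, where the slope test does well. Under AR(1) with complete data the problem vanishes. No aim is framed around change between months 18 and 24.

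Much of this stands. The size and sign of the error are unknown in advance, and the largest effects need erosion of the benefit. The month 18-24 comparison is an addition suited to the design's stated purpose, not a repair of a promised test.

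It does not remove the point. A gap that keeps growing need not grow linearly, and a slope is the natural target only for a rate-of-change hypothesis, which this trial does not state. Blinded covariance selection protects against choosing a favourable result, but the choice still determines how the visits are weighted.

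**Conclusion.** The concern holds and should be fixed. In the supplied text the primary test does not target the quantity in the endpoint, hypothesis and sample size unless the arms diverge linearly or the weighting happens to favour months 0 and 24. In the main case, with a true month-24 difference of 2.5 kg, the reported effect runs from 1.9 to 2.9 kg across the assumed paths. Power runs from 65% to 94%, against a steady 84-85% for the contrast. Where the effect fades after month 18, the slope can overstate what remains (1.8 kg against 1.25 kg in path 6).

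These figures rest on assumed paths, an assumed residual SD of 1.5-2.5 kg, dropout completely at random and the plan's SD, correlation and ICC. No figure is offered for Aim 2, which inherits the model and may use generalised mixed models. Section 18 lists a separate Statistical Analysis Plan that was not supplied, so the finding is about the wording of section 10.2 and may already be settled there.

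**What to change.** In Aim 1, treat time as categorical (0, 6, 12, 18, 24) with a full arm-by-time interaction. Name one primary test: the arm difference in change from month 0 to month 24, with its estimate and 95% confidence interval. Report the month 18-24 change in the arm difference from the same model as a secondary sustainability result (SE about 0.39-0.58 kg in the main case). Keep the linear-interaction model as secondary. Make the same change for Aim 2. If the separate Statistical Analysis Plan already defines a month-24 contrast, reconcile section 10.2 with it.

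The cost is wording only, with no change in sample size. If divergence is truly linear, power falls by about 1-3 points under the starting model (main case: 86% to 84-85%; complete data: 82-84% to 80.5%). Under compound symmetry it falls by 7-8 points (main case: 90% to 83%; complete data: 88% to 81%). Power stays above 80% in each case, though with complete data the margin is only about half a point.

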Behavioral interventions that involve dietary modification and physical activity, combined with cognitive and behavioral strategies, are efficacious for short-term weight loss but less so for long-term weight loss. Several randomized trials indicate that various dietary approaches (e.g., low-carbohydrate diet, low-fat/low-calorie diet) are efficacious for inducing short-term weight loss.(14, 15) A systematic review indicated that supplementing dietary modification with physical activity improves 12-month outcomes above diet alone.(16) Incorporating behavioral strategies such as self-monitoring, stimulus control, action planning, and problem-solving helps promote adherence to these lifestyle behaviors.(14, 17) Following significant weight loss, most people tend to regain 1-2 kg per year, with the majority of people returning to baseline weight by 5 years.(17) Various strategies have been evaluated to reduce weight regain, including sequential dieting, meal replacements, medications, and behavioral approaches.(18) These strategies have not reduced the overall pattern of regain for most people.(17) Furthermore, research indicates that the best predictor of long-term weight loss is greater initial weight loss.(19) This research suggests that long-term weight loss will be enhanced by 1) identifying efficacious strategies to enhance maintenance and 2) increasing the amount of initial weight loss.

One way to improve long-term weight loss is to increase the effectiveness of social support. Decades of observational research indicates that people with greater social support—often measured by marital status as a proxy—live longer and have better health.(20) Because domestic partners share eating habits, physical activity patterns, and other health behaviors, there are frequent opportunities for partners to provide each other with informational, emotional, and instrumental support.(21) Furthermore, domestic partners are the preferred source of support for most people.(22, 23) Despite the positive effects noted in observational research, trials of weight loss interventions involving spouses/partners have not yielded uniformly positive effects.(24)

[figure not shown]

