Taken together, previous research indicates a possible benefit to including partners in weight loss efforts but underscores the need for rigorous research on efficacy that builds on modern theoretical frameworks. Trials are needed that (1) are rigorous in design and implementation; (2) address weight loss initiation and maintenance; (3) systematically train couples to communicate about health and train partners in strategies for providing effective support for health behavior change; (4) isolate the partner intervention to provide a stringent test; and (5) evaluate theoretically specified mediators. This study accomplishes each of these.

Framing a health problem as “our” problem can initiate communal coping responses to promote health behavior change. The domestic partnership can be leveraged to help initiate and maintain behavior change. According to Lewis’ interdependence model of communal coping and behavior change,(37) couples who approach behavior change as a problem to be tackled together versus independently (referred to as ‘transformation of motivation’) are more likely to utilize effective communal coping processes, including higher levels of (1) outcome efficacy (i.e., a couple’s beliefs about the utility of communal coping for improving health), (2) couple efficacy (i.e., a couple’s confidence that they can engage in communal coping efforts), and (3) use of communal coping strategies (i.e., communicating about and coordinating actions relevant to the health problem, such as joint decision making and planning regarding health behavior and identifying and practicing methods of providing informational, emotional, and instrumental support). Our intervention is designed to affect these interdependence constructs to improve long-term weight loss and associated health behaviors (Figure 1). We will measure these constructs so that we can empirically assess the extent to which they mediate the effect of our partner-assisted intervention on long-term weight loss.

Figure 1. Conceptual Model Based on Interdependence Theory

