## 6. Study Objectives and Purpose

[figure not shown]
- Primary objective: To assess 24-month long-term weight loss in a patient-only vs. partner-assisted intervention.
- Secondary objective: To assess 24-month long-term self-reported patient caloric intake and physical activity in a patient-only vs. partner-assisted intervention.
- Exploratory objective: The role of theoretically hypothesized mediators of intervention effects will be examined, including transformation of motivation, couple efficacy, outcome efficacy, use of communal coping, and social support for physical activity and dietary intake at 24 months.

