#### **Patient weight loss maintenance intervention (months 7-18, both arms)**

Patients will transition to the behavioral maintenance intervention in month 7 regardless of whether they achieved their 6-month weight loss goal for 3 reasons: 1) It is not feasible for some patients to continue the group-based initial protocol while others transition to the individual maintenance protocol; 2) Based on previous studies, most patients achieve maximum weight loss at 6 months; 3) Our maintenance protocol allows for patients to continue pursuing weight loss during the maintenance phase if desired. The protocol also stipulates that patients who relapse (gain > 3lb.) should revert to creating dietary and physical activity goals and monitoring these behaviors, thus re-focusing on weight loss. In months 19-24, patients will not receive intervention but will be encouraged to continue self-monitoring using the provided devices. This transition mimics real-world practice in which patients would be expected to apply the maintenance skills they have learned once intervention contacts cease. The 6-month period without intervention contact will allow examination of the sustainability of intervention effects.

The maintenance intervention was designed to help patients transition from the intensity that characterizes most weigh loss interventions to the real world in which patients rarely have further intervention-related contact. This intervention involves a shift from diet initiation content to maintenance-oriented skills training, then switches mode from in-person to telephone, and finally decreases contact frequency. The interventionist will place all telephone calls using a semi-structured script programmed into a custom intervention program that records participant responses for reference in subsequent calls. There will be a 2-week window around the target call date. If the educator is unable to contact a patient in the call window, then that telephone call will be skipped. Continuity will be maintained because each call involves a review of data from the previous call and a review of the same behavioral skills. All maintenance telephone calls will be audio recorded. [name] will meet with [name] and the interventionists weekly to review a random subset of recorded calls and provide feedback using a checklist.

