
where *trt* is the treatment indicator and *t* is linear time, then the null hypothesis is  $H_0: \beta_3 = 0$ . In addition, we will tabulate the analysis results for the (fixed) effects of the baseline covariates such as patient sex, patient BMI, and partner BMI.

**Aim 2: Test the hypotheses that average daily caloric intake is significantly lower, and frequency of moderate intensity physical activity is significantly greater, in the partner-assisted arm than the patient-only arm at 24 months.** Dietary adherence will be operationalized as daily intake of calories at months 0, 6, 12, 18, and 24. For each of these same assessment times, physical activity will be summarized as the total and mean minutes of moderate levels per week. Changes in dietary adherence and physical activity will be analyzed using the same methods and models as presented for the Aim 1 analyses of weight loss. Previous experience with these outcomes has shown they are often non-normally distributed; therefore, outcomes may be analyzed as generalized linear mixed models, estimated with adaptive Gaussian quadrature, as needed. As exploratory analyses, we will use the models described for Aims 1 and 2 to examine "spillover" effects(34) of the partner-assisted intervention on partner weight and dietary adherence.(50)

**Aim 3: Assess the extent to which interdependence constructs (transformation of motivation, couple efficacy, outcome efficacy, use of communal coping) mediate the effect of the partner-assisted weight management intervention on weight loss.** We will estimate the extent to which the effect of the partner intervention,  $T_i$  on participants' weight at 6 months,  $Y_i$ , is jointly mediated by a vector of five mediating constructs,  $M_i = (M_{i1}, \dots, M_{i5})$  measured at 3 months: transformation of motivation, couples' efficacy, outcome efficacy, use of communal coping, and social support. Each mediating construct is measured by the summary scale of associated items. We will assess mediation twice: separately for the diet and physical activity domains of the mediators.

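### The exploratory mediation objective names 24 months, but the only mediation model given uses month-3 mediators and month-6 weight; the printed indirect-effect contrast is also reversed

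*Combined protocol and SAP*

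**What the plan says.** **Objective.** The exploratory objective in Section 6 lists the constructs to be examined as mediators and ends with "use of communal coping, and social support for physical activity and dietary intake at 24 months". Section 5.1 says the constructs will be measured to assess how far "they mediate the effect of our partner-assisted intervention on long-term weight loss". Section 7.1.1 fixes the term: "The primary outcome is long-term weight loss, defined as patient weight at 24 months". Aim 3 in Section 2 and H3 in Section 5.2 give no time point.

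**Model.** Section 10.2, Aim 3, takes five constructs measured at month 3 and estimates the joint mediation of the intervention effect "on participants' weight at 6 months". The definition of the direct effect repeats month 6. The analysis is done once for the diet domain and once for the physical activity domain, with baseline controls B.

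**Indirect effect.** The same section defines the natural indirect effect as E[Y(0,M(0)) − Y(0,M(1))|B] and sets it equal to b11·a21 + … + b15·a25.

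**Schedule.** Table 2 (Section 9.2), as extracted, appears to mark the mediators at every wave including month 24. The visit narrative in Section 9.2.1 and Table 7 in Section 9.2.3 do not list them at month 24.

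**The concern.** Section 7.1 states: "This design addresses long-term weight loss, which results from both initial weight loss and weight loss maintenance". It also expects that "incorporating partners in both phases is likely to have greater impact on long-term weight loss than incorporating partners in either phase alone". A mediation result for month-6 weight speaks only to the first of those phases. Followed as written, the text reviewed gives no analysis for the time point its own exploratory objective names, although month-24 weight will be collected. Without a label, the month-6 result could be reported as the answer to the 24-month objective.

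The reversed contrast is a smaller matter. Definition and estimator have opposite signs. Anyone working from the definition rather than from the coefficients would report the indirect effect with the wrong sign, and the direct and indirect effects as defined would not add up to the total effect.

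**Working it through.** **1. Time points side by side.** The phrase in Section 6 can be read in two ways.

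| Reading of Section 6 | Needs | Section 10.2 model has |
|---|---|---|
| Effects at 24 months | weight at month 24 | weight at month 6 |
| Mediators measured at 24 months | mediators at month 24 | mediators at month 3 |

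Neither reading is met. Section 5.1, read with Section 7.1.1, supports the first.

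**2. Sign of the indirect effect.** Inputs are the two regressions in Section 10.2:

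- E[Y|T,M,B] = a0 + a1·T + Σ a2k·Mk + a3·B
- E[Mk|T,B] = b0k + b1k·T + b2k·B

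Substituting the second into the first:

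- Printed contrast: E[Y(0,M(0)) − Y(0,M(1))|B] = Σ a2k·(b0k − b0k − b1k) = −Σ b1k·a2k. The plan prints plus, so its identity does not reproduce.
- Swapped contrast: E[Y(0,M(1)) − Y(0,M(0))|B] = +Σ b1k·a2k. This matches the printed right-hand side.
- Direct effect: E[Y(1,M(0)) − Y(0,M(0))|B] = a1, as printed.
- Total effect: a1 + Σ b1k·a2k.

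Illustration with invented coefficients b1 = (0.3, 0.4, 0.2, 0.5, 0.3), a2 = (−0.6, −0.5, −0.8, −0.6, −0.7) and a1 = −1.50 kg:

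- Σ b1k·a2k = −0.18 − 0.20 − 0.16 − 0.30 − 0.21 = −1.05 kg
- total effect = −1.50 − 1.05 = −2.55 kg
- direct effect + printed contrast = −1.50 + 1.05 = −0.45 kg
- direct effect + swapped contrast = −2.55 kg

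These values show the inconsistency; they do not forecast a result.

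**3. Precision of a month-24 run.** Plan inputs (Section 10.1): 230 patients, 20% attrition, SD 19.9 kg, month 0–24 correlation 0.96. So n = 230 × 0.8 = 184 and residual SD = 19.9 × √(1 − 0.96²) = 5.57 kg. Assumptions not in the documents: true indirect effect −1.0 kg shared equally by five standardised mediators, intercorrelation 0.5, and arm shift d of 0.2, 0.3 or 0.5 SD on each.

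With a2k = −0.2/d, the variance has three parts:

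- from the b coefficients: (4/184) × 15 × 0.04/d² = 0.01304/d²
- from the a coefficients: (5.57²/184) × d² × 5/3 = 0.281·d²
- product term: 5 × 4 × 5.57²/184² = 0.0183

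| d | Sum | Closed-form SE | Simulated SE | 95% half-width (1.96 × simulated SE) |
|---|---|---|---|---|
| 0.2 | 0.326 + 0.011 + 0.018 | 0.60 | 0.59 | 1.16 kg |
| 0.3 | 0.145 + 0.025 + 0.018 | 0.43 | 0.44 | 0.86 kg |
| 0.5 | 0.052 + 0.070 + 0.018 | 0.38 | 0.38 | 0.75 kg |

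The simulation used 3,000 trials per setting. With a true effect of −1.0 kg, normal-approximation power at these SEs is about 40%, 62% and 75%.

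**4. Early weight change before month 3.** Table 3 lists two group sessions in each of months 1 to 3, so six weigh-ins. The first supplies the baseline weight (Section 9.2.1), leaving at most 5 after baseline. The ±14-day survey window in Table 7 may leave fewer.

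**5. Month-24 mediators.** Table 2 appears to include them; Section 9.2.1 and Table 7 do not. Table 7's month-24 row also omits the COVID-19 survey that Section 9.2.1 lists, so that row is incomplete in at least one respect and is weak evidence on its own.

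**The case against.** The model is explicit and coherent: mediators precede the outcome, and month 6 is stated twice, so it is not a slip. The plan supports an early outcome. Section 5.1 notes that "research indicates that the best predictor of long-term weight loss is greater initial weight loss", and Section 9.2.2 says: "Based on previous studies, most patients achieve maximum weight loss at 6 months". Aim 3 and H3 name no time point, and the phrase in Section 6 may describe mediator measurement, which would fit Table 2. All of this stands. It makes the month-3/month-6 model defensible, but it does not give either reading of Section 6 an analysis.

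It can also be said that month-24 runs with month-3 mediators contain no mediator measured during maintenance, and that they are imprecise. Both points are right. At the smallest assumed shift the half-width (1.16 kg) exceeds the assumed effect (1.0 kg). Narrowing the objective's wording is therefore a legitimate alternative. Later mediators are not an easy substitute: they follow months of weight change that the intervention may have affected, which strains the plan's own assumption (ii).

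Finally, there may be material outside the text reviewed. Section 18 lists a Statistical Analysis Plan. Section 11.2.2.1 points to an exploratory-aim model said to follow, but none does. A reader might infer that no 24-month mediation analysis exists anywhere. The documents show its absence only from the text reviewed.

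**Conclusion.** The point holds in limited form and is minor, since it concerns an exploratory aim only. In the text reviewed, the 24-month objective has no matching mediation analysis, and the printed indirect-effect contrast has the opposite sign to its estimator.

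Three stronger inferences are not supported:

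- *That the month-6 mediation model is invalid.* It is a valid initiation-phase analysis under its stated assumptions.
- *That the trial would report mediation with the wrong sign.* Code written from the coefficient sum gives the right answer; only the definition is transposed.
- *That the main results are at risk.* The primary and secondary analyses do not use this model.

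The sign result is algebra and needs no assumed values. The precision range of 0.75 to 1.16 kg rests on the assumed effect, shifts and intercorrelation given in the working.

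**What to change.** 1. Label the current model as mediation of 6-month weight (initiation phase), and do not report it as answering the 24-month objective.
2. Add exploratory runs of the same regressions, one for each domain, with month-24 weight as outcome and the same month-3 mediators and baseline controls. If the separate Statistical Analysis Plan already holds such a model, cross-reference it instead. If the sponsor does not want these runs, restrict the wording in Sections 6 and 5.1 to 6-month weight. If the runs are added, state that:
   - they test only whether early mediator change carries through to 24 months;
   - pathways arising later fall into the direct effect;
   - precision is low;
   - month-3 mediators may themselves follow early weight change, so assumption (ii) is a caveat for the month-6 and month-24 outcomes alike.
3. Rewrite the indirect effect as E[Y(0,M(1)) − Y(0,M(0))|B] = Σ b1k·a2k, so that direct plus indirect equals total.
4. Reconcile Table 2 with Section 9.2.1 and Table 7 on month-24 mediators, and Table 7 with Section 9.2.1 on the COVID-19 survey.

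**Cost.** Wording changes plus two further runs of the same code on data already scheduled, with no new visits. The month-24 runs are less precise than the month-6 ones. From sample size alone the SE is larger by √(230/184) − 1 = 11.8% if nobody is lost by month 6, and by nothing if all 20% are lost by then; the documents give no month-6 attrition. If month-6 weight is also more tightly tied to baseline (assumed correlation up to 0.98), the simulated loss reaches about 35% with no month-6 attrition.
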